APPENDIX C. DEFINITIONS OF CARDIOGENIC SHOCK, SEVERE SEPSIS AND SEPTIC SHOCK [9]

Cardiogenic shock is a cardiac disorder that results in both clinical and biochemical evidence of tissue hypoperfusion [10]. The definition of cardiogenic shock may be clinically determined and consists of the following: Systolic blood pressure (SBP) < 90 mmHg for at least 30 minutes, OR

- Hemodynamic support required to maintain SBP \geq 90 mmHg, AND
- End-organ hypoperfusion (e.g., urine output < 30 mL/hr or cool extremities)

Cardiogenic shock may also be optionally defined by hemodynamic criteria obtained through invasive hemodynamic monitoring:

- Cardiac index \leq 2.2 L/min/m², AND
- Pulmonary capillary wedge pressure \geq 15 mmHg

Severe sepsis is defined as sepsis-induced tissue hypoperfusion or organ dysfunction with any of the following thought to be due to the infection:

- Sepsis-induced hypotension
- Lactate above upper limit of normal (ULN)
- Urine output < 0.5 mL/kg/hr for more than 2 hours despite adequate fluid resuscitation
- Acute lung injury with partial pressure oxygen-arterial (PaO₂)/fraction of inspired oxygen (FIO₂) < 250 in the absence of pneumonia as infection source
- Acute lung injury with PaO₂/FIO₂ < 200 in the presence of pneumonia as infection source
- Creatinine > 2 mg/dL (176.8 micromol/L)
- Bilirubin > 4 mg/dL (34.2 micromol/L)
- Platelet count < 100,000 microL⁻¹
- Coagulopathy (International normalized ratio [INR] > 1.5)

Sepsis-induced tissue hypoperfusion is defined as infection-induced hypotension, elevated lactate, or oliguria.

Sepsis-induced hypotension is defined as a SBP < 90 mmHg, or mean arterial pressure (MAP) < 70 mmHg, or a SBP decrease > 40 mmHg, or less than 2 standard deviations below normal for age in the absence of other causes of hypotension.

Septic shock is defined as sepsis-induced hypotension (as defined above) persisting despite adequate fluid resuscitation.

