10.3.4. Clinical Laboratory Testing

Blood specimens for routine chemistry and hematology will be obtained at selected time points (see [Appendix A](#)).

The following assays will be performed at the Local Laboratory:

- Hematology: hemoglobin, hematocrit, white blood cell (WBC) count, platelet count, WBC differential
- Coagulation: prothrombin time reported as the INR

- Serum Chemistry: sodium, potassium, chloride, carbon dioxide (bicarbonate), glucose, blood urea nitrogen, creatinine, aspartate aminotransferase, alanine aminotransferase, alkaline phosphatase, and total, direct, and indirect bilirubin
- Serum or urine pregnancy test (in women of child bearing potential; see [Appendix D](#))

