--	--	--	--	--

	
11. The patient was treated with an investigational drug < 30 days prior to Screening.
 
12. Prior treatment with andexanet.
	
screening.
 
8.9. The patient has severe sepsis or septic or severe hemorrhagic shock at the time of Screening.
 
10. The patient has heparin-induced thrombocytopenia (with or without thrombosis).
 
11. Inherited coagulopathy (e.g., anti-phospholipid antibody syndrome, protein C/S deficiency, Factor V Leiden)
 
12. Last dose of apixaban < 2.5 mg, rivaroxaban < 10 mg, edoxaban < 30 mg, or enoxaparin 40 mg.
 
9.13. The patient is pregnant or a lactating female.
 
10.14. The patient has received any of the following drugs or blood products within 7 days of enrollment:
 
 o Vitamin K antagonist antagonists (e.g., warfarin). o Dabigatran. o Prothrombin complex concentrate products (e.g., Kcentra®) or recombinant factor VIIa (e.g., NovoSeven®). o Whole blood, plasma fractions. 
Note: Administration of tranexamic acid, platelets or packed red blood cells is not an exclusion criterion.
 
11.15. The patient was treated with an investigational drug < 30 days prior to Screening.
 
12.16. Prior treatment with andexanet.
		
Synopsis, Test Product, Dose, and Mode of Administration	The andexanet IV bolus will be initiated within 30 minutes prior to the start of surgery (i.e., the first incision). The bolus will be followed by a continuous infusion lasting 120 minutes, irrespective of the	The andexanet IV bolus will be initiated within 30 minutes prior to the start of surgery (i.e., the first incision) → and must be completed prior to surgery start. The bolus will be followed by a continuous infusion	Clarified dosing and surgery details and timing. Clarified	S

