4.2. Exclusion Criteria

If a patient meets any of the following criteria, he or she is *not* eligible to participate:

1. Surgery predicted to last > 4 hours or for which the risk of clinically meaningful uncontrolled or unmanageable bleeding is low.
2. Acute life-threatening bleeding at the time of Screening.
3. Any surgical procedure requiring cardiopulmonary bypass, an intra-aortic catheter, or the intra-operative use of systemic, intravascular, unfractionated heparin.
4. Expected survival of < 1 month due to comorbidity.
5. Existing “Do Not Resuscitate” order or similar advanced directive.
6. The patient has a recent history (within 30 days prior to Screening) of a diagnosed TE as follows: VTE (including DVT, PE, intracardiac thrombus); myocardial infarction (including asymptomatic troponin elevations); disseminated intravascular coagulation (DIC); acute traumatic coagulopathy; cerebrovascular accident; transient ischemic attack; unstable angina pectoris hospitalization; or severe peripheral vascular disease (see [Appendix B](#) for DIC scoring algorithm).
7. Acute decompensated heart failure or cardiogenic shock at the time of screening (see [Appendix C](#) for cardiogenic shock definition)

8. The patient has severe sepsis or septic or hemorrhagic shock at the time of Screening (see definition in [Appendix C](#)).
9. The patient is pregnant or a lactating female.
10. The patient has received any of the following drugs or blood products within 7 days of enrollment:
 - VKA (e.g., warfarin).
 - Dabigatran.
 - Prothrombin complex concentrate products (PCC, e.g., Kcentra[®]), recombinant factor VIIa (rfVIIa) (e.g., NovoSeven[®]).
 - Whole blood, plasma fractions.
 - Note: Administration of tranexamic acid (TXA), platelets, or packed red blood cells (PRBCs) is not an exclusion criterion.
11. The patient was treated with an investigational drug < 30 days prior to Screening.
12. Prior treatment with andexanet.

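### Appendix C gives the severe-sepsis bilirubin cut-off as two values that differ by a factor of two, so one exclusion criterion is ambiguous for a narrow group of patients

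*Protocol*

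**What the plan says.** Appendix C defines severe sepsis as sepsis-induced tissue hypoperfusion or "organ dysfunction with any of the following thought to be due to the infection". Nine findings follow. The bilirubin line is "Bilirubin > 4 mg/dL (34.2 micromol/L"), and the creatinine line in the same list is "Creatinine > 2 mg/dL (176.8 micromol/L"). Both lines read the same in the original protocol and in Amendment 1.

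The definition is used for eligibility. Section 4.2 of the original protocol (criterion 8) excludes a patient if "The patient has severe sepsis or septic or hemorrhagic shock at the time of Screening" and refers to Appendix C. Amendment 1's own Section 4.2 is not in the part of the document at hand, but its summary of changes (Appendix G) keeps the exclusion, renumbered 9: "The patient has severe sepsis or septic or severe hemorrhagic shock at the time of Screening".

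On measurement, Section 10.3.4 states "The following assays will be performed at the Local Laboratory". The serum chemistry panel listed there includes "alkaline phosphatase, and total, direct, and indirect bilirubin", with no reporting unit fixed. Appendix A places chemistry in the same screening window as the eligibility decision. Section 10.1.7 says that the sponsor grants no exceptions or waivers on eligibility.

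**The concern.** The bracketed figure is presented as the SI equivalent of the mg/dL figure. If it is not, the protocol holds two different rules under one exclusion criterion and does not say which governs. Because one finding is enough to define severe sepsis, the bilirubin line can decide eligibility by itself.

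At stake is whether a patient in the gap is eligible. An investigator, monitor or auditor could not tell from the text whether enrolling that patient was a deviation. Whichever value was intended, use of the other misclassifies. If the mg/dL value was intended, the SI value turns away eligible patients. If the SI value was intended, the mg/dL value admits patients who were meant to be excluded.

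**Working it through.** **Inputs from Appendix C.** Bilirubin: 4 mg/dL and 34.2 micromol/L. Creatinine: 2 mg/dL and 176.8 micromol/L.

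**Inputs from chemistry, not in the protocol.** Molar masses follow from the molecular formulas, with atomic masses C 12.011, H 1.008, N 14.007 and O 15.999:

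- Bilirubin, C33H36N4O6: 396.363 + 36.288 + 56.028 + 95.994 = 584.67 g/mol.
- Creatinine, C4H7N3O: 48.044 + 7.056 + 42.021 + 15.999 = 113.12 g/mol.

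**Formula.** micromol/L = mg/dL × 10,000 / molar mass. One mg/dL is thus 10,000 / 584.67 = 17.10 micromol/L for bilirubin and 10,000 / 113.12 = 88.40 micromol/L for creatinine.

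**Control: creatinine.** 2 × 88.40 = 176.8 micromol/L. This reproduces the protocol's figure, so the method matches the one used for the list.

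**Bilirubin.**

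- 4 mg/dL: 4 × 17.10 = 68.4 micromol/L. The protocol's 34.2 is not reproduced.
- 34.2 micromol/L: 34.2 / 17.10 = 2.0 mg/dL.
- Ratio of the two printed cut-offs: 68.4 / 34.2 = 2.00.
- For 34.2 to be right, the molar mass would have to be 4 × 10,000 / 34.2 = about 1,170 g/mol, twice that of bilirubin. Rounding cannot explain the gap.

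**Who is affected.** The two values classify a patient differently only if all of these hold:

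1. An infection is present.
2. Bilirubin is above 34.2 and up to 68.4 micromol/L (above 2 and up to 4 mg/dL).
3. The raised bilirubin is thought to be due to the infection.
4. None of the other eight findings is met: hypotension, raised lactate, low urine output, the two lung-injury items, creatinine, platelets, INR.

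Such a patient has severe sepsis under the SI value, and is excluded. Under the mg/dL value the same patient does not have it, and this criterion does not exclude.

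**The case against.** The strongest reply accepts the arithmetic and disputes the reach. The four conditions must hold together, attribution to infection is a judgement, and a patient with infection and raised bilirubin may well meet another listed finding. This stands. The affected group is narrow, and the documents give no way to count it.

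A reader might infer more in three ways, none of which the documents support:

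- **That enrolment and safety risk vary by country.** The original synopsis plans about 120 sites in North America, Europe and Rest of World, and Amendment 1 keeps the number. Mixed reporting units are therefore plausible. But no section states which unit any site reports, or that sites using SI units would apply the bracketed figure. No safety consequence can be shown either, since the intended value is unknown and the SI value is the one that excludes more patients.
- **That the planned share of abdominal surgery measures the impact.** Amendment 1 plans about 20% abdominal cases. That figure covers all abdominal operations, infected or not, and says nothing about bilirubin in the gap. A bilirubin raised for another reason, such as obstruction, would not count under the attribution wording.
- **That every infected patient in the gap is classified differently.** This ignores the attribution condition and the other eight findings.

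It can also be objected that the explicit reference to Appendix C is seen only in the original protocol's Section 4.2. That is correct. The link very probably persists, because Amendment 1 retains both the exclusion and the Appendix C definition, but it cannot be read directly in the part at hand.

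**Conclusion.** The point holds: wrong as written, and minor. Appendix C prints two bilirubin thresholds that differ by a factor of 2.00 as if they were one, in a definition that an exclusion criterion relies on, and nothing in the document at hand says which is meant. The neighbouring creatinine conversion is correct.

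The effect is confined to the narrow group set out in the check. Its size is not derivable and is probably small. The sample-size calculation and the primary analysis do not use this threshold and are unaffected.

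The conclusion rests on the molar mass of bilirubin, which needs no cited source, and on the exclusion still pointing to Appendix C under Amendment 1. A practical difference between sites further assumes that reporting units are mixed. The documents do not show which of the two values was intended, and this review takes no position on that.

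**What to change.** The sponsor should reconcile the two figures to one intended bilirubin threshold and derive the other unit from it at 17.1 micromol/L per mg/dL. Appendix C should then be corrected and sites told which value applies.

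Any patient screened with a bilirubin above 34.2 and up to 68.4 micromol/L should have the eligibility classification re-checked against the reconciled value, with attribution to infection and the other listed findings taken into account.

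The change to the text is one figure. A site notice alone is not enough, because Section 13.6 requires protocol changes to be made by amendment, approved by the sponsor and the ethics body before they take effect. The correction can travel with the next amendment. The re-check is limited to screened patients in that bilirubin range.

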APPENDIX D. DEFINITION OF FEMALE OF CHILDBEARING POTENTIAL

All women of childbearing potential (including those who have had a tubal ligation) will have a urine or serum pregnancy test at screening. If the pregnancy test is positive, andexanet should not be administered.

All female patients are considered to be of childbearing potential unless they meet 1 of the following criteria:

1. The patient has been post-menopausal (amenorrheic) for at least 1 year
2. The patient had a surgical bilateral oophorectomy (with or without hysterectomy) more than 6 weeks prior to screening
3. The patient had a hysterectomy

APPENDIX E. GUIDANCE FOR SUBMISSION OF POTENTIAL THROMBOTIC EVENTS FOR ADJUDICATION

Adjudication criteria for the diagnosis transient ischemic attacks, strokes, myocardial infarctions (MIs), venous thromboembolism, and arterial systemic embolism are provided below.

Transient Ischemic Attack (TIA) is defined as a transient episode of neurological dysfunction caused by focal brain, spinal cord, or retinal ischemia, with signs or symptoms lasting < 24 hours and no evidence of new infarct on neuroimaging if performed. Investigators should consider submitting cases for adjudication if an event meets this definition.

Stroke is defined as an acute episode of neurological dysfunction consistent with a vascular cause. A stroke will be considered to have occurred if there is a rapid onset of signs and/or symptoms of a new persistent neurological deficit consistent with an obstruction to cerebral blood flow with no apparent nonischemic cause (e.g., trauma, tumor, or infection). Signs or symptoms must last at least 24 hours or, for symptom onset less than 24 hours, have neuroimaging evidence of new infarct. Available neuroimaging studies will be considered to support the clinical impression and to determine if there is a demonstrable lesion compatible with an acute stroke. For the diagnosis of stroke, the following criteria must be fulfilled:

- Rapid onset of a focal/global neurologic deficit with at least 1 of the following: change in level of consciousness, hemiplegia, hemiparesis, numbness or sensory loss affecting 1 side of the body, dysphagia/aphasia, hemianopia, amaurosis fugax, or other new neurological signs/symptoms consistent with stroke.
- The duration of a focal/global neurologic deficit is at least 24 hours, OR the neurological deficit results in death, OR there is neuroimaging evidence of a new infarct.
- There is no other readily identifiable non-stroke cause for the clinical presentation (e.g., brain tumor, trauma, infection, hypoglycemia, peripheral lesion).
- Confirmation of the diagnosis by at least 1 of the following: specialist evaluation, or brain imaging procedure (i.e., computed tomography [CT] scan, magnetic resonance imaging [MRI] scan, cerebral vessel angiography).

If the acute neurological signs represent a worsening of a previous (baseline) deficit, the new signs must have either persisted for more than 1 week, or persisted for more than 24 hours and were accompanied by an appropriate new imaging finding.

Investigators should consider submitting cases for adjudication as a possible stroke if they meet 1 or more of the above criteria, or have potential symptoms and/or conditions (e.g., delirium, mental status changes) that are not otherwise explainable by an alternative etiology.

Since the adjudication of hemostatic efficacy encompasses changes in clinical neurologic function and hematoma volume, these findings will only be considered for thrombotic event adjudication if they clearly have an ischemic etiology.

Myocardial Infarction (MI) should be used when there is evidence of myocardial necrosis in a clinical setting consistent with acute myocardial ischemia. Under these conditions any one of the following criteria meets the diagnosis of MI:

- Detection of a rise and/or fall of cardiac biomarker values (preferably cardiac troponin [cTn]) with at least 1 value above the upper limit of normal (ULN) and with at least 1 of the following:
 - Symptoms of ischemia
 - New or presumed new significant ST-segment-T wave (ST-T) changes or new left bundle branch block
 - Development of pathological Q waves in the electrocardiogram (ECG)
 - Imaging evidence of new loss of viable myocardium or new regional wall motion abnormality
 - Identification of an intracoronary thrombus by angiography or autopsy
- Cardiac death with symptoms suggestive of myocardial ischemia and presumed new ischemic ECG changes or new left bundle branch block (LBBB), but death occurred before biomarkers were obtained, or before cardiac biomarker values would be increased
- Percutaneous Coronary Intervention (PCI) related MI is arbitrarily defined by elevation of cTn values ($> 5 \times$ ULN) in patients with normal baseline values or a rise of cTn values $> 20\%$ if the baseline values are elevated and are stable or falling. In addition, either (i) symptoms suggestive of myocardial ischemia, (ii) new ischemic ECG changes, (iii) angiographic findings consistent with a procedural complication, or (iv) imaging demonstration of new loss of viable myocardium or new regional wall motion abnormality are required.
- Stent thrombosis associated with MI when detected by coronary angiography or autopsy in the setting of myocardial ischemia and with a rise and/or fall of cardiac biomarker values with at least 1 value above the ULN
- Coronary artery bypass grafting (CABG) related MI is arbitrarily defined by elevation of cardiac biomarker values ($> 10 \times$ ULN) in patients with normal baseline cTn values. In addition, either (i) new pathological Q waves or new LBBB, (ii) angiographic documented new graft or new native coronary artery occlusion, or (iii) imaging evidence of new loss of viable myocardium or new regional wall motion abnormality.

Investigators should consider submitting cases for adjudication as a possible MI if they meet 1 or more of the above criteria, or have potential symptoms and/or conditions (e.g., angina,

ventricular tachyarrhythmia, cardiogenic shock, heart failure) that are not otherwise explainable by an alternative etiology.

Venous Thromboembolism is defined as a symptomatic deep vein thrombosis (DVT) or PE confirmed by objective testing. Criteria for the objective confirmation of DVT include:

- A constant filling defect in 2 or more views on contrast venography in 1 or more proximal venous segments (iliac, common femoral, superficial femoral, popliteal)
- New or previously undocumented non-compressibility of 1 or more venous segments on compression ultrasound
- A clearly defined intraluminal filling defect on contrast enhanced CT

Criteria for the objective confirmation of PE include:

- An intraluminal filling defect on pulmonary angiography
- Sudden contrast cut-off of 1 or more vessels more than 2.5 mm in diameter on a pulmonary angiogram
- A high probability ventilation-perfusion (VQ) scan (1 or more segmental perfusion defects with corresponding normal ventilation)
- An abnormal non-high VQ scan plus criteria for the diagnosis of DVT
- An unequivocal, intra-arterial, un-enhancing filling defect in the central pulmonary vasculature (pulmonary trunk, main pulmonary arteries, anterior trunk, right and left interlobar and lobar arteries) on CT

Investigators should consider submitting cases for adjudication as a possible VTE if they meet 1 or more of the above criteria, or have potential symptoms and/or conditions (e.g., lower extremity swelling, respiratory failure) that are not otherwise explainable by an alternate etiology. All cases of unexplained sudden death should also be submitted for adjudication as a possible PE and/or MI.

Arterial systemic embolism is defined as abrupt vascular insufficiency associated with clinical and other objective evidence of arterial occlusion in the absence of other likely mechanisms. Clinical signs and symptoms must be consistent with embolic arterial occlusion, and there must be clear evidence of abrupt occlusion of a systemic artery, with at least 1 type of supporting evidence, such as surgical report indicating evidence of arterial embolism, pathological specimens related to embolism removal, imaging evidence consistent with arterial embolism, or autopsy report. Investigators should consider submitting potential systemic arterial embolism cases for adjudication if they meet this definition.

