11.5. Efficacy Endpoints and Analyses

11.5.1. Definitions

Hemostasis will be assessed from the start of surgery to the end of the procedure. Categories for the assessment of intraoperative hemostasis are provided in Table 3.

Table 3: Intraoperative Hemostasis Categories

Category	Definition
Excellent	Normal hemostasis during the procedure
Good	Mildly abnormal hemostasis as judged by quantity or quality of blood loss (e.g., slight oozing from surgical wounds)
Moderate	Moderate abnormality in intraprocedural hemostasis (e.g., controllable bleeding) but no need for additional systemic procoagulant products *
Poor	Severe hemostatic abnormality during the procedure (e.g., severe refractory hemorrhage) and need for additional systemic procoagulant products *

* Tranexamic acid excluded.

The evaluation period for anti-fXa activity covers the period of time from 5 minutes following the end of the andexanet bolus to just prior to the end of the andexanet infusion. The baseline measurement will be the last value obtained prior to andexanet treatment.

The hemostasis evaluation would exclude unexpected blood loss due to surgical complications that may cause uncontrolled bleeding, such as unintended injury of a major vessel or parenchymal tissue.

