11.5.2. Efficacy Endpoints

11.5.2.1. *Primary Efficacy Endpoint*

The primary efficacy endpoint is the achievement of effective hemostasis, as determined by the surgeon's assessment of intraoperative hemostasis and confirmed by adjudication by an independent EAC (see Table 3).

For each patient, hemostasis will be considered to be effective if the intraoperative hemostasis category is Excellent or Good, and ineffective if the intraoperative hemostasis category is Moderate or Poor.

A patient will be deemed non-evaluable if s/he meets the criteria specified in the EAC Charter.

11.5.2.2. *Secondary Efficacy Endpoint*

The secondary efficacy endpoint is the percent change in anti-fXa activity from baseline to the evaluation period nadir. The evaluation period starts 5 minutes after the end of the andexanet bolus and ends just prior to the end of the andexanet infusion.

Patients who do not have at least 1 anti-fXa activity level within the evaluation period will have percent decrease imputed as 0.0% (i.e., using the baseline value as the nadir value).

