11.7.2. Thrombotic Events

All TEs will be assessed by the EAC and summarized descriptively, including whether patients were re-anticoagulated prior to the event.

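### Appendix E sets a clearly-ischemic test for neurologic changes on a ground that does not apply in this trial, so strokes or TIAs of uncertain cause could drop out of the thrombotic event count

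*Protocol*

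**What the plan says.** Appendix E of the Protocol tells investigators which events to send to the EAC as possible thrombotic events (TEs). For stroke, cases should be considered if they meet one or more of the listed criteria, or "have potential symptoms and/or conditions (e.g., delirium, mental status changes) that are not otherwise explainable by an alternative etiology".

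The next paragraph adds a restriction: "these findings will only be considered for thrombotic event adjudication if they clearly have an ischemic etiology". The reason it gives, in the opening clause of the same sentence, is this: "Since the adjudication of hemostatic efficacy encompasses changes in clinical neurologic function and hematoma volume". The sentence stands in both the original protocol and the amended text.

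The efficacy sections define hemostasis differently from what that reason assumes. Section 11.5.1 states: "Hemostasis will be assessed from the start of surgery to the end of the procedure". Section 11.5.2.1 makes the primary endpoint the surgeon's "assessment of intraoperative hemostasis and confirmed by adjudication by an independent EAC".

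On safety, Section 11.7 lists TEs within 30 days of enrollment, both suspected and confirmed. Section 11.7.2 says: "All TEs will be assessed by the EAC and summarized descriptively". Section 8.2 (shown in the original version; Appendix G lists no change to it) refers investigators to Appendix E when they decide whether to submit an event, and counts every submitted event as a suspected TE.

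**The concern.** The restriction is justified by the idea that another endpoint already captures these findings. If that endpoint does not capture them, a postoperative neurologic deficit of uncertain cause can be turned away from TE adjudication without being picked up in hemostatic efficacy.

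TEs are the only adverse event of special interest in Section 9.1.3, and Section 3.5 treats them as a foreseeable risk of reversing anticoagulation. A rule that asks for more certainty than the stroke definition can move the count in one direction only: down, or not at all. Ambiguous neurologic findings are realistic here. Section 11.9 names neurosurgical procedures as a subgroup, and Section 10.3.2 foresees neurologic examination for spinal cord compression.

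**Working it through.** This is mainly a comparison of texts. The plan gives no figure for the effect of the sentence, so there is none to reproduce.

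**1. Does hemostatic efficacy cover neurologic function or hematoma volume?**
- Window: incision to final skin closure (Sections 10.4.1 and 11.5.1). A deficit noticed after surgery falls outside it.
- Content: the four categories of Table 3 describe the degree of bleeding and the need for systemic procoagulants. The Good category, for example, reads "Mildly abnormal hemostasis as judged by quantity or quality of blood loss (e.g., slight oozing from surgical wounds". No category mentions neurologic function or hematoma volume.
- Adjudication: the EAC confirms this intraoperative rating (Section 11.5.2.1). Section 12.0 lists post-surgical bleeding as a separate adjudication task, and Section 3.1 of the original version places surgical hematomas there.

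In the text shown, the stated reason therefore does not apply.

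**2. Is the test consistent with the rest of Appendix E?**

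| Place in Appendix E | Standard for a neurologic event |
|---|---|
| Stroke definition | Works by exclusion: no cause other than ischemia is apparent or readily identifiable. A deficit of at least 24 hours qualifies without a new infarct on imaging, and a specialist evaluation can confirm it. |
| Submission guidance for stroke | One listed criterion, or an unexplained symptom such as delirium, is enough to consider submission. |
| The restricting sentence | The etiology must be clearly ischemic. |

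A specialist-confirmed deficit lasting at least 24 hours, with no visible infarct and no other cause found, meets the stroke definition but can fail the restricting sentence.

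**3. Which counts are exposed?**
- If the EAC applies the test when it confirms events, the confirmed count is exposed and the suspected count is intact.
- If a site applies it when deciding on submission, the event never becomes a suspected TE, and both counts are exposed.

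**4. Scale, for illustration only**
- Planned enrollment: about 200 (Section 11.6). Taking all 200 as treated, one patient lost from the count = 1/200 = 0.5 percentage point.
- Reference rate: 34 of 352 patients in the earlier acute-bleeding study (Section 1.4.7). 34/352 = 9.66%, which agrees with the stated 9.7%.
- Expected patients with a TE at that rate: 200 × 0.0966 = 19.3.
- Patients lost = 19.3 × cerebral share × share withheld. Neither share is in the documents. I assume 20% to 60% for the first and 0% to 50% for the second.

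| Cerebral share | Share withheld | Patients lost | Rate as counted |
|---|---|---|---|
| any | 0% | 0 | 9.66% |
| 20% | 50% | 1.93 | 8.69% |
| 40% | 25% | 1.93 | 8.69% |
| 40% | 50% | 3.86 | 7.73% |
| 60% | 50% | 5.80 | 6.76% |

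The table assumes that every withheld event would otherwise have been confirmed and was the patient's only TE. It shows sensitivity and is not an estimate.

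**The case against.** The strongest reply is that the sentence may do little or nothing.

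- **It can be read as inert.** It restricts findings that the efficacy adjudication covers. If there are none, nothing is restricted. This is a fair literal reading, but it gives no reason to keep the sentence, and sites and the EAC cannot be relied on to infer it.
- **It names no decision-maker.** The appendix opens by describing its content as adjudication criteria, so the EAC may be the one to apply the test. Submission and the suspected count would then be untouched. The conflict with the stroke definition at confirmation would remain.
- **Stroke and TIA are already ischemic by definition.** Hemorrhagic deficits are rightly not TEs. This stands, and it limits the exposure to deficits of uncertain cause.
- **Not all governing text is shown.** The EAC Charter and the first part of the amended protocol are not at hand. Appendix G records an addition to Section 7.3 under which EAC-confirmed post-surgical bleeding counts as poor hemostatic efficacy, so efficacy may reach beyond the Table 3 rating. Even so, that addition introduces neither neurologic function nor hematoma volume.

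A reader might infer that uncertain neurologic deficits are recorded nowhere. The documents do not support this. The submission route remains in the text, submitted events count as suspected TEs, and new deficits are recorded as adverse events through Day 30. A reader might also infer that a control arm would have exposed the loss, but a control arm under the same rule would share it.

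**Conclusion.** The sentence rests on a ground that does not apply in the text shown, and it conflicts with the stroke definition and the submission guidance beside it. Strokes or TIAs of uncertain etiology could be left out of the confirmed TE count, and out of the suspected count as well if sites treat the sentence as a filter.

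The size cannot be derived from the documents and may be nil. What can be said is 0.5 percentage point per patient lost at 200 treated, with any bias toward fewer events. The 9.7% reference covers all types of TE in a cohort of which 64% had intracranial hemorrhage, so it is a scale for illustration and not a forecast for surgical patients.

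It is tempting to conclude that strokes and TIAs will be under-counted, by a stated amount, and that the trial cannot proceed unchanged. That goes too far: the number withheld would be a bare assumption, only uncertain cases are exposed, TE results are descriptive, and the primary endpoint, the analysis populations and the sample size are unaffected. The point should be fixed, but it is not critical.

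**What to change.** Delete the sentence from Appendix E. If the sponsor prefers to keep a statement there, replace it with one that reconciles the standards:

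- any new neurologic event meeting a listed stroke or TIA trigger is submitted and counted as a suspected TE;
- the EAC decides etiology, using the stroke and TIA criteria already in Appendix E.

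If the EAC Charter repeats the sentence, align it. The cost is a short text change and a few more cases for the existing EAC. No endpoint, analysis or clinical management rule changes.
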